## 5. SAFETY ASSESSMENTS

Safety data will be summarized for the all treated population. Table 3 summarizes the safety analyses to be performed.

Adverse events will be coded in accordance with the MedDRA. Severity of AEs will be graded by the investigator according to the NCI-CTCAE v4.03 for non-hematological AEs and IWCLL 2008 guidelines for hematologic toxicity.

Treatment emergent period is defined as the period from the date of the first dose of study treatment up to 30 days after the date of the last dose of study treatment or the day before initiation of subsequent antineoplastic therapy or reintroduction of study treatment, whichever comes first.

The treatment emergent adverse events (TEAE) are those events that occur or worsen during the treatment-emergent period or that are related to the study treatment. Unless otherwise specified, only TEAEs will be included in the adverse event summaries. For MRD cohort, TEAEs within first 16 cycles (pre-randomization phase) and overall treatment emergent period (pre-randomization and randomization phase) will be both summarized.

All laboratory values will be converted to and reported in international system of units (SI). Hematologic parameters including platelet counts, hemoglobin, and neutrophils will be assessed by the grading scale for hematologic toxicity in CLL studies in the IWCLL 2008 guidelines. All other gradable laboratory parameters will be graded using the NCI CTCAE v4.03. Unless otherwise specified, only baseline and post-baseline values collected during the treatment-emergent period will be included in the safety analysis.

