10.4.11. Safety Analysis

In the MRD cohort, analysis of safety data will be conducted on the all treated population in pre-randomization phase and safety population in the randomization phase. An overall summary across both pre-randomization and randomization phase may also be provided as appropriate. The baseline value is defined as the last value collected on or prior to the first dose date of study drug. In the Fixed Duration cohort, safety analysis will be based on all treated population.

The safety variables to be analyzed include exposure of study drugs, AEs, clinical laboratory test results (hematology and chemistry), ECOG performance, physical examination, and vital signs measurements. In general, continuous variables will be summarized using descriptive statistics (n, mean, median, standard deviation, standard error and range). Categorical variables will be summarized using frequencies and percentages. No formal statistical testing is planned.

Adverse Events

Adverse event parameters to be evaluated are the type, incidence, and intensity of AEs; the relationship of AEs to study treatment; and the action taken with respect to study treatment due to AEs.

The verbatim terms used in the eCRF by investigators to identify AEs will be coded using the Medical Dictionary for Regulatory Activities (MedDRA).

Treatment-emergent period is defined as the period of time from the first dose of study treatment, until the earlier of:

- Thirty days following the last dose of ibrutinib or 30 days following the last dose of venetoclax, whichever occurs later

AND

- The start date of a new anti-cancer therapy.

The treatment-emergent AEs (TEAEs) are those events that:

- Are not present prior to the treatment-emergent period and occur during the treatment-emergent period,
- The onset dates are missing, and end dates are during the treatment-emergent period,
- Are considered related to study drug by the investigator regardless of the start dates of the events, or
- Are present prior to the treatment-emergent period but worsen in severity during the treatment-emergent period or are subsequently considered related to study drug by the investigator.

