Appendix C. Schedule of Assessments for Reintroduction of Ibrutinib (MRD and FD Cohorts)

Study Visits	Every 4 months for the first year, then every 6 months until PD (Day 1 of each visit)	Suspected PD (as soon as possible after suspected PD)	End-of-Treatment 30 Days ^k	Post PD Follow-up (Every 4 months)
Study Visit Windows	±3 days	Any time	±3 days	±14 days
Study Drug Administration and Dispensation				
Ibrutinib	Ibrutinib: 420 mg PO daily			
Procedures				
Medical Monitor approval	Obtained before 1 st dose			
Study Drug Compliance Review ^b	X	X	X	
Concomitant medications	X	X	X	
Adverse events ^a	X	X	X	
Physical exam, vital signs, weight, ECOG ^c	X	X	X	
Overall response assessment	X	X		
CT/MRI scan ^d	X (at the end of 4 months, at the end of 12 months, and annually thereafter)	X		
Bone marrow biopsy/aspirate for response (local lab and central lab)	X (only if suspected CR / to confirm CR)	X (if clinically indicated)		
Hematology (local lab) ^h	X	X	X	
Serum chemistry (local lab) ^h	X	X	X	
Creatinine clearance (eg, Cockcroft-Gault) ^h	X (1 st visit only)			
Coagulation panel ^h	X (1 st visit only)			
IGHV (central lab) ^f	X (1 st visit only)			
Karyotype (central lab) ^g	X (1 st visit only)			
FISH (local or central lab) ^e	X (1 st visit only)			
Survival status, including other malignancies				
Survival status, including other malignancies				X
Any new anti-cancer therapy				
Any new anti-cancer therapy				X
12-lead ECG ⁱ	X (prior to reintroduction and then as clinically indicated) (eg, subjects with palpitations, lightheadedness)			
ECHO or MUGA scan ^j	X (prior to reintroduction and then as clinically indicated)			

Footnote:

- a. Adverse Events: AEs are reported from the time the subject restarts study drug until 30 days following last dose of study drug. In addition to all routine AE reporting, all new malignant tumors including solid tumors, skin malignancies and hematologic malignancies are to be reported as adverse events.
- b. Study Drug Compliance: Includes subject instruction and routine review of study drug diary and evaluation of contents of study drug containers from home administration
- c. Physical Exam: Vital signs will be collected through end of treatment only. ECOG collected through disease progression.

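### The SAP closes the treatment-emergent period the day before reintroduction, so adverse events not attributed to study drug, and all laboratory values, on reintroduced drug drop out of its safety tables

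*SAP*

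**What the plan says.** SAP section 5 closes the treatment-emergent period at the earliest of three dates: 30 days after the last dose, the day before the start of any later antineoplastic regimen "or reintroduction of study treatment, whichever comes first". It defines treatment-emergent events as "those events that occur or worsen during the treatment-emergent period or that are related to the study treatment". As the default rule for the tables, "only TEAEs will be included in the adverse event summaries", and for laboratory data "only baseline and post-baseline values collected during the treatment-emergent period will be included in the safety analysis". For the MRD cohort, events in the first 16 cycles and in the "overall treatment emergent period (pre-randomization and randomization phase) will be both summarized".

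Protocol 10.4.11 also ends its period at the earlier of two dates, but they differ. One is "Thirty days following the last dose of ibrutinib or 30 days following the last dose of venetoclax, whichever occurs later"; the other is the start of new anti-cancer therapy. Reintroduction is not mentioned. The protocol undertakes to analyse all treatment-emergent events and, like the SAP, confines laboratory summaries to its period unless otherwise specified.

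Reintroduced ibrutinib and venetoclax are study drug (Protocol 8.4), and Protocol 3.1 makes reintroduction part of the MRD cohort's randomization phase. Safety data are collected then: under Appendix C, "AEs are reported from the time the subject restarts study drug until 30 days following last dose of study drug", and Appendices D and E carry the same rule.

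SAP section 6 lists one change from the protocol, a matter of terminology.

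**The concern.** The two documents give different periods, and the difference falls on time when subjects are taking study drug. Reintroduction can mean a fresh venetoclax ramp-up, for which the protocol requires TLS risk assessment and management, or a return to ibrutinib, before which the protocol asks for an ECG and an echocardiogram or MUGA scan. The protocol thus treats retreatment as a period needing safety attention, while the SAP's readable safety section gives it no window and no table.

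At stake is whether the study report describes the safety of retreatment under the same capture rule as the first course. Before reintroduction, every adverse event in the period counts. Afterwards, an event counts only if the investigator attributes it to study drug. A rate built on both rules is hard to interpret, and attribution is a weak filter when the first course tables do not depend on it.

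**Working it through.** No sample size, power or event count bears on this point, so there is no figure to reproduce. The check sets the definitions side by side.

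1. *Is reintroduced time inside the protocol's period?* Yes. Reintroduced drug is study drug, the period ends 30 days after the later last dose of either agent, and only new anti-cancer therapy closes it sooner.

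2. *Is it inside the SAP's period?* No, whichever way the last dose is read. If it means the last dose of the first course, the period has closed by 30 days after that dose at the latest. If it means the last dose of all, the reintroduction clause closes the period first.

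3. *What happens to each kind of observation made after the first reintroduced dose?*

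| Observation | Protocol 10.4.11 | SAP section 5 and Table 3 |
|---|---|---|
| New adverse event, not called related | Treatment-emergent | Excluded |
| Adverse event called related | Treatment-emergent | Treatment-emergent through the relatedness limb, which has no date limit; table placement unclear in the MRD cohort |
| Serious event, not called related | Treatment-emergent | Ambiguous: Table 3 lists SAEs with no window, the text admits only treatment-emergent events unless otherwise specified |
| Laboratory value | Included | Excluded; no relatedness exception |

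Placement in the second row is unclear because the MRD cohort's wider summary covers the overall treatment-emergent period, which has already closed for a reintroduced subject.

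4. *Events of special interest.* Protocol 11.4.6.1 requires a major hemorrhage to be treatment-emergent under each of its three limbs. Under the SAP's period, one that occurs on reintroduced drug and is not called related may not meet that definition.

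5. *Subjects who never stop.* Under Protocol 3.1.2, ibrutinib-arm subjects of the MRD cohort, whether randomized as MRD-negative or MRD-positive, continue ibrutinib and add venetoclax. Their SAP period closes while ibrutinib exposure is uninterrupted.

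6. *Time outside the period, per subject.* Reintroduced venetoclax in the MRD cohort: up to 2 years per course. Repeat of the fixed-duration regimen in the FD cohort: 15 cycles × 28 days = 420 days. Reintroduced ibrutinib alone: no fixed end. These are ceilings, not expected values.

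**The case against.** The strongest reply is that the SAP's cut-off is sensible. It matches the general analysis period in SAP section 4, which also ends at reintroduction, and it keeps events of placebo subjects who restart ibrutinib from being counted under placebo. The protocol's definition is not a perfect benchmark: applied across courses, it makes the whole off-drug gap treatment-emergent, and Protocol 3.1.3 requires that gap to exceed 2 years before the combination is repeated in the FD cohort. Protocol section 10 calls its own methods a general description. All of this stands, and it is why the window should be kept for the first course. It does not explain the absence of a window for the second, or of an entry in section 6.

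Three stronger readings are tempting and are not supported.

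- *That all adverse events on reintroduced drug disappear.* The relatedness limb keeps those attributed to study drug, whatever their date.
- *That TLS on a new ramp-up would go unreported.* The protocol describes TLS as a known on-target effect of venetoclax, so an investigator could be expected to call it related, and it would be kept. What is lost is the laboratory picture, including uric acid, creatinine clearance and gradable chemistry.
- *That serious events and deaths are dropped.* Table 3 names SAEs separately and allows listings, the protocol allows narratives, and overall survival counts death from any cause. For unrelated serious events the text is ambiguous, which is a lesser fault.

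A retreatment analysis might also exist elsewhere. Exploratory text is blacked out, and Protocol 10.4.3 allows a pooled ibrutinib-retreatment analysis under a separate SAP. That provision is optional, sits under response rate and does not cover reintroduced venetoclax, so it does not settle the matter. The SAP also plans about 5 years of FD follow-up where this protocol plans about 10, so it may have been written against another protocol version. Whether that version defined the period in the same way cannot be checked here.

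**Conclusion.** The point holds in limited form. Under the rules as written, two things leave the SAP's safety tables once study drug is reintroduced: adverse events not attributed to it, and all laboratory values. Two more are left unclear: where related events are tabulated in the MRD cohort, and whether unrelated serious events are kept. The departure from Protocol 10.4.11 is not declared in SAP section 6.

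The size in subjects or events cannot be stated, because the documents do not give the number reintroduced. By the FD primary analysis, repeat combination exposure may be small: the last subject needs only 15 post-treatment cycles (420 days) of follow-up, against the more than 2 years to progression required before that regimen is repeated. Neither primary endpoint is affected.

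The conclusion assumes that the readable SAP text is complete on safety and that no separate retreatment plan fills the gap. It is worth correcting because the stated rule, if followed, omits data from time on study drug.

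**What to change.** Keep the SAP's window for the first course, and make these changes.

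- In section 5 and Table 3, define a reintroduction window from the first reintroduced dose to the earlier of 30 days after the last dose and the day before new antineoplastic therapy.
- Give it its own baseline. Appendix L grades platelets and hemoglobin by percentage fall from the pre-treatment value, so the choice of baseline changes the grades.
- Summarise, by reintroduced regimen: adverse events, SAEs, grade 3 or worse events, events of special interest, TLS, discontinuations, deaths and laboratory values.
- State that related events with onset after reintroduction are tabulated in this window and not in the first-course tables.
- List the departure from Protocol 10.4.11 in section 6.

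The cost is SAP wording and a few extra descriptive tables. The data are already collected under Appendices C, D and E.

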**Table 3: Summary of Safety Assessments**

Assessment Type	Definition	Analysis Methods
AE	TEAEs, SAEs, Grade 3 or worse TEAEs, related TEAEs, TEAEs leading to treatment discontinuation, TEAEs leading to dose reduction, TEAEs leading to death, protocol- defined events of special interest and other safety observations.	Descriptive summary statistics and/or listings
Lab	Worst post-baseline toxicity grade for selected gradable hematology and chemistry. Abnormalities in creatinine clearance, uric acid, and liver function.	Descriptive summary statistics and/or listings
Vital Signs	Blood pressure, heart rate	Descriptive summary statistics and/or listings

TEAE= treatment emergent adverse event; SAE= serious adverse event.

## **6. CHANGES IN PROTOCOL PLANNED ANALYSIS**

- The term “MRD-negative response” was replaced by the phrase “MRD negativity”.

